4.0 STUDY DESIGN

4.1 Overall Design

This is a Phase 1a, single center, double-blind, placebo-controlled, randomized, single ascending-dose first-in-human (FIH) study. The study will recruit up to 40 healthy normal participants, aged 18 to 55 years inclusive, with standard inclusion/exclusion criteria for healthy participant studies. Up to 5 cohorts of 8 participants (6 active, 2 placebo participants per cohort) will be enrolled with each participant assigned to receive a single dose of CS-1103 or placebo on 1 occasion (Day 1).

All participants will be screened within 28 days of dose administration and participants will check-in to the inpatient clinical research unit (CRU) on Admission/Day –1. Participants will be randomized on Day –1, the day prior to their schedule CS-1103 administration (after meeting all eligibility criteria). Participants are scheduled to remain in the CRU for up to 48 hours postdose for safety and PK assessments. Participants will be discharged on Day 3 after completion of all scheduled assessments and will be asked to return to the CRU on Day 8 for the end of study (EOS) visit. Note: Discharge from the CRU may be delayed for up to 8 hours to optimize PK assessment (see [Section 8.4.1](#)). The study duration will be approximately 37 days.

All participants for a dose level may check-in to the CRU on the same date. However, each dose level will include 2 sentinel participants (1 active, 1 placebo) who will be dosed first and monitored by an Investigator for a minimum of 24 hours. The available safety and tolerability data from the sentinel participants, up to 24 hours post dose, will be reviewed by an Investigator. Following this safety data review, dosing of the remaining participants in the cohort may proceed (see [Section 10.1.7.1](#)). The remaining participants for each dose level will be randomized the day prior to dosing and will dose on Day 1, provided there are no safety or tolerability concerns, using a 5:1 randomization ratio to active or placebo study treatment separately for each dose level. A randomization list will be prepared for each cohort. See [Section 4.5](#) for dose escalation details.

Eligible participants will be randomized to 5 cohorts of 8 participants each. Each cohort will receive a single IV infusion of CS-1103 or placebo at one dose level. At each dose level, 6 participants will receive CS-1103 and 2 participants will receive matching placebo. The starting dose and provisional subsequent dose levels are provided below:

- Cohort 1: Dose level 1 (CS-1103 2.7 mg/kg, [REDACTED]) or placebo ([REDACTED])
- Cohort 2: Dose level 2 (CS-1103 8.0 mg/kg, [REDACTED]) or placebo ([REDACTED])
- Cohort 3: Dose level 3 (CS-1103 16.0 mg/kg, [REDACTED]) or placebo ([REDACTED])
- Cohort 4: Dose level 4 (CS-1103 26.7 mg/kg, [REDACTED]) or placebo ([REDACTED])
- Cohort 5: Dose level 5 (CS-1103 40.0 mg/kg, [REDACTED]) or placebo ([REDACTED])

[figure not shown]
- Note: The dose will be capped at 3000 mg.

4.2 Scientific Rationale for Study Design

This is the FIH study to be conducted with CS-1103. It is designed to evaluate the safety, tolerability, and PK of CS-1103 in healthy participants at increasing doses when given as a single IV infusion. The study will be conducted in healthy participants who are free of underlying comorbidities to allow evaluation of CS-1103-related response. The schedule of safety and PK assessments and planned 48-hour in-house observation are targeted to an expected short half-life ($t_{1/2}$) based on the nonclinical species evaluated. The 7-day follow-up period is consistent with that of other FIH studies.

[figure not shown]
Scheduled activities during the Phase 1a clinical trial include careful monitoring of vital signs (systolic, diastolic, and mean blood pressure, pulse rate, respiratory rate, oxygen saturation, body temperature) and electrocardiogram (ECG) monitoring before, during, and after dosing. The proposed monitoring plan mitigates any potential risk for the Phase 1a clinical trial associated with respiratory or cardiovascular effects.

[figure not shown]
4.3 Justification for Dose

CONFIDENTIAL

Protocol CS-1103-01, Version 3.0 Amendment 2

Additional details are provided in the current IB.

4.4 End of Study Definition

The end of the study is defined as the date of the last visit of the last participant in the study or last scheduled procedure shown in the schedule of activities (SoA) ([Section 1.3](#)), whichever is later.

A participant is considered to have completed the study if he/she has completed all periods of the study including the last visit or the last scheduled procedure shown in the SoA [Section 1.3](#).

4.5 Dose Escalation

This initial dose will be a single IV infusion. An expected dose escalation will proceed with maximum incremental increase in dose not exceeding 3-fold at the lowest dose. Subsequent dose escalation will not exceed a 2-fold increase in dose and the incremental dose escalations are planned to decrease in size as CS-1103 dose rises. See [Section 4.1](#) for the provisional CS-1103 doses for the subsequent cohorts and for additional details on screening and admission/discharge from the inpatient CRU.

Dose escalation to the next dose level(s) will not proceed until the safety and tolerability of CS-1103 over at least 48 hours and plasma PK results scheduled over at least the 24 hour in-clinic assessment period have been evaluated for at least 6 of the 8 participants in the preceding dose cohort by the Safety Review Committee (SRC) (see [Section 10.1.7.1](#)).

² At a dose of 40.0 mg/kg CS-1103 in humans, the C_0 is estimated at 340 $\mu\text{g}/\text{mL}$ (220 μM) and $\text{AUC}_{[0-\text{last}]}$ is estimated at 318 $\mu\text{g}\cdot\text{hr}/\text{mL}$.

4.6 Study Stopping Criteria

4.6.1 Criteria for Stopping Dose Escalation

Dose escalation will be stopped if any of the following study stopping rules are met:

- One or more participants who received CS-1103 report a serious adverse events (SAEs) considered at least possibly related to the study treatment
- Two or more participants who received CS-1103 experience a moderate AE in the same organ system that are at least possibly related to the study treatment
- One or more participants who received CS-1103 fulfill Hy's law defined as alanine aminotransferase (ALT) or aspartate aminotransferase (AST)] $>3 \times$ the upper limit of normal (ULN) and total bilirubin $>2 \times$ ULN in the absence of significant increase ($>2 \times$ ULN) in alkaline phosphatase (ALP) and in the absence of an alternative diagnosis that explains the increase in total bilirubin, to be assessed from the first administration of study treatment up to and including follow-up/EOS Visit. The event must be considered at least possibly related to study treatment
- Two or more participants, who receive CS-1103, have QTc prolongation defined as QT corrected for heart rate by Fridericia's formula (QTcF) >500 msec, or an increase of QTcF >60 msec above baseline to a value >480 msec on the 12-lead ECG, confirmed (persistent for >5 min) on a repeat 12-lead ECG.
- Any other event in CS-1103-treated participants occurs and is deemed by the SRC to pose an unacceptable risk to participants
- Any participant exceeds predicted exposures equivalent to exposure limits [REDACTED]; AUC_(0-last) (456 $\mu\text{g}\cdot\text{h}/\text{mL}$). If the predefined exposure limits are reached and there are no safety or tolerability concerns, a lower dose may be investigated. If any of these criteria are met, the SRC will stop further dose escalation. The SRC will determine whether a lower dose should be tested or whether the study should be terminated

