10.1.7 Committees Structure

10.1.7.1 Safety Review Committee

A SRC has been appointed for this study. The SRC is a group of clinicians and/or scientists who are appointed to monitor the safety and scientific integrity of a human research intervention, and to make recommendations regarding for escalation to the next planned dose level, escalation to an intermediate dose (a dose lower than the next planned dose), repeating a dose level, suspension of the dose escalation until further review of study data can be made, as to whether the stopping rules have been met, or stop dose escalation and termination of the study, etc. The composition of the committee is dependent upon the scientific skills and knowledge required for monitoring the particular study.

The SRC will consist, at a minimum, of the Principal or Sub-Investigator, Medical Monitor, and Sponsor's qualified designee. The SRC is responsible for reviewing and evaluating blinded safety and PK data for the most recently dosed cohort, cumulatively obtained data, and subsequently at regularly scheduled meetings and for the dose selection during dose escalation. The committee may also meet in ad hoc meetings at its discretion as needed in response to events occurring in the study.

Participant safety will be continuously monitored by the SRC, which includes safety signal detection at any time during the study.

In addition, an early aggregated safety data review will be performed, the goal of which is to allow for a cautious, stepwise approach to study treatment administration/dose escalation. An initial sentinel safety review by an Investigator for this study is planned for the first 2 participants who are dosed in each of the 5 cohorts and have provided safety and tolerability data for 24 hours after administration of a single dose prior to dosing the remaining participants within each cohort (see [Section 4.1](#)).

All safety results for at least 48 hours and preliminary PK data through at least Day 2 (24 hours postdose) for at least 6 out of the 8 participants within a cohort will be summarized

and reviewed by the SRC for agreement of next steps in dose escalation, due to the short half-life of the compound.

In particular, data will be reviewed by the Sponsor for identification of events that would potentially contribute to a requirement to pause/stop dose escalation or the study. See [Section 4.6](#) for stopping criteria details.

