10.3.2 Definition of SAE

An SAE is defined as any untoward medical occurrence that, at any dose, meets one or more of the criteria listed:

a. Results in death
 
• For SAEs with the outcome of death, the date and cause of death will be recorded on the appropriate case report form.

b. Is life-threatening
 
• The term life-threatening in the definition of serious refers to an event in which the participant was at risk of death at the time of the event. It does not refer to an event, which hypothetically might have caused death, if it were more severe.

c. Requires inpatient hospitalization or prolongation of existing hospitalization
 
• In general, hospitalization signifies that the participant has been admitted (usually involving at least an overnight stay) at the hospital or emergency ward for observation and/or treatment that would not have been appropriate in the physician's office or outpatient setting. Complications that occur during hospitalization are AEs. If a complication prolongs hospitalization or fulfills any other serious criteria, the event is serious. When in doubt as to whether hospitalization occurred or was necessary, the AE should be considered serious.• Hospitalization for elective treatment of a preexisting condition that did not worsen from baseline is not considered an AE.

d. Results in persistent or significant disability/incapacity
 
• The term disability means a substantial disruption of a person's ability to conduct normal life functions.• This definition is not intended to include experiences of relatively minor medical significance such as uncomplicated headache, nausea, vomiting, diarrhea, influenza, and accidental trauma (e.g., sprained ankle) that may interfere with or prevent everyday life functions but do not constitute a substantial disruption.

e. Is a congenital anomaly/birth defect
 
• The term congenital anomaly/birth defect means there is suspect that exposure to a medical product prior to conception or during pregnancy may have resulted in an adverse outcome in the child.

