
f. Other situations:
 
• Medical or scientific judgment should be exercised by the Investigator in deciding whether SAE reporting is appropriate in other situations such as significant medical events that may jeopardize the participant or may require medical or surgical intervention to prevent one of the other outcomes listed in the above definition. These events should usually be considered serious.

- Examples of such events include invasive or malignant cancers, intensive treatment for allergic bronchospasm, blood dyscrasias, convulsions or development of intervention dependency or intervention abuse.

AE and SAE Recording

- When an AE/SAE occurs, it is the responsibility of the Investigator to review all documentation (e.g., hospital progress notes, laboratory reports, and diagnostics reports) related to the event.
- The Investigator will then record all relevant AE/SAE information.
- It is **not** acceptable for the Investigator to send photocopies of the participant's medical records to the Sponsor or designee in lieu of completion of the applicable/required report form.
- There may be instances when copies of medical records for certain cases are requested by the Sponsor or designee. In this case, all participant identifiers, with the exception of the participant number, will be redacted on the copies of the medical records before submission to the Sponsor or designee.
- The Investigator will attempt to establish a diagnosis of the event based on signs, symptoms, and/or other clinical information. Whenever possible, the diagnosis (not the individual signs/symptoms) will be documented as the AE/SAE.

Assessment of Intensity

The intensity of an AE is an estimate of the relative severity of the event made by the Investigator based on his or her clinical experience and familiarity with the literature. The following definitions are to be used to rate the severity of an AE:

- Mild: Asymptomatic or mild symptoms; clinical or diagnostic observations only; intervention not indicated.
- Moderate: Minimal, local, or noninvasive intervention indicated; limiting age-appropriate instrumental Activities of Daily Living (ADL). Instrumental ADL refers to preparing meals, shopping for groceries or clothes, using the telephone, managing money, etc.

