- Severe: Severe or medically significant but not immediately life-threatening; hospitalization or prolongation of hospitalization indicated; disabling, limiting self-care ADL. Self-care ADL refers to bathing, dressing and undressing, feeding self, using the toilet, taking medications, and not bedridden.

Assessment of Causality

- The Investigator is obligated to assess the relationship between study treatment and each occurrence of each AE/SAE. The Investigator will use clinical judgment to determine the relationship.
- A *reasonable possibility* of a relationship conveys that there are facts, evidence, and/or arguments to suggest a causal relationship, rather than a relationship cannot be ruled out.

- Alternative causes, such as underlying disease(s), concomitant therapy, and other risk factors, as well as the temporal relationship of the event to study treatment administration, will be considered and investigated.
- For causality assessments, events assessed as having a reasonable possibility of being related to study treatment will be considered "related". Events assessed as having no reasonable possibility of being related to study treatment will be considered "unrelated".
- The Investigator will also consult the IB and/or product information, for marketed products, in his/her assessment.
- For each AE/SAE, the Investigator **must** document in the medical notes that he/she has reviewed the AE/SAE and has provided an assessment of causality.
- There may be situations in which an SAE has occurred and the Investigator has minimal information to include in the initial report to the Sponsor or designee. However, it is very important that the Investigator always makes an assessment of causality for every event before the initial transmission of the SAE data to the Sponsor or designee. All SAEs shall be considered at least possibly related to the study drug unless there is an obvious alternative explanation for the event.
- The Investigator may change his/her opinion of causality in light of follow-up information and send an SAE follow-up report with the updated causality assessment.
- The causality assessment is one of the criteria used when determining regulatory reporting requirements.

Follow-up of AEs and SAEs

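### The adverse-event rule for stopping dose escalation names only moderate events, so severe non-serious related events do not count toward the mandatory stop

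*Protocol*

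**What the plan says.** Protocol Section 4.6.1 lists the criteria for stopping dose escalation. The adverse-event criterion is met when "Two or more participants who received CS-1103 experience a moderate AE in the same organ system that are at least possibly related" to study treatment. The consequence is not discretionary: "If any of these criteria are met, the SRC will stop further dose escalation".

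The other criteria are one related serious adverse event (SAE), Hy's law, confirmed QTcF prolongation in two or more participants, an exposure limit, and a catch-all: "Any other event in CS-1103-treated participants occurs and is deemed by the SRC to pose an unacceptable risk to participants". None of them names severe adverse events.

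The intensity grades are defined in Appendix 3 (Section 10.3.2, Assessment of Intensity). Moderate begins with "Minimal, local, or noninvasive intervention indicated" and includes limits on instrumental daily activities. Severe is a separate, higher grade, beginning with "Severe or medically significant but not immediately life-threatening" and including limits on self-care. SAP Section 16.1.1.1 uses the same three ordered grades.

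**The concern.** A stopping rule should respond at least as strongly to a worse signal. This one, followed as written, does not: two moderate events force a stop, while replacing either with a severe non-serious event removes it. Severe non-serious events can then halt escalation only if the SRC first judges the risk unacceptable, a step that two moderate events do not need.

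This is a first-in-human study whose primary objective is safety and tolerability, and Protocol Section 2.3 relies on the stopping criteria to protect participants. A pre-specified trigger is there to take discretion out of the decision. Here discretion comes back only for the worse events.

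**Working it through.** **Does any text supply the missing grade?** The plan states no operating characteristic for this rule, so there is no figure to reproduce. The check is first one of wording.

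- Section 4.6.1 names one grade, with no phrase meaning at least moderate.
- Sections 6.5, 7.0 and 10.1.7.1 refer back to Section 4.6 or describe general SRC powers. None adds severe events to the rule.
- Seriousness is defined separately from severity, by outcome (Section 10.3.2). SAP Section 16.1.1.2 lists severe and serious as separate items in the overall summary, so the plan expects them to differ.

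**What the rule does.** Take related, non-serious events in one organ system in two different CS-1103 participants, each with events of one grade only:

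| Participant 1 | Participant 2 | Rule as written | With severe included |
|---|---|---|---|
| moderate | moderate | stop | stop |
| severe | moderate | no stop | stop |
| severe | severe | no stop | stop |

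A participant with both a moderate and a severe event in the organ system still counts as written.

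**Size, given that participants are affected.** Let M be the number of participants with at least one related moderate event in the organ system, and S the number with a related severe non-serious event and no moderate event there. As written the rule fires if M ≥ 2; corrected, if M + S ≥ 2. Suppose k participants are affected and each is independently severe-only with probability s. The rule misses when M is 0 or 1:

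P(miss) = s^k + k·s^(k−1)·(1 − s)

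For k = 2 this equals 1 − (1 − s)². At s = 10% it is 1 − 0.81 = 0.190. For k = 3 at s = 10% it is 0.001 + 3 × 0.01 × 0.9 = 0.028.

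| s (assumed) | k = 2 | k = 3 |
|---|---|---|
| 5% | 0.098 | 0.007 |
| 10% | 0.190 | 0.028 |
| 20% | 0.360 | 0.104 |

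These hold whether events are counted within a cohort or across cohorts.

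**Size without that condition.** Section 4.1 gives 6 active participants per cohort and up to 5 cohorts, so 5 × 6 = 30 in all. Section 4.6.1 does not say whether counting is per cohort or cumulative, and Section 10.1.7.1 has the SRC "reviewing and evaluating blinded safety and PK data for the most recently dosed cohort, cumulatively obtained data", so both are shown. With independent participants and one rate p at every dose,

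P(fires) = 1 − (1 − p)^n − n·p·(1 − p)^(n−1)

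As written, p is the moderate rate; corrected, p is the moderate rate plus the severe-only rate. For n = 6 and p = 0.10: 1 − 0.531 − 0.354 = 0.114 after rounding.

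| Moderate (assumed) | n | As written | Corrected, severe-only 1% | 2% | 5% |
|---|---|---|---|---|---|
| 10% | 6 | 0.114 | 0.134 | 0.156 | 0.224 |
| 10% | 30 | 0.816 | 0.857 | 0.890 | 0.952 |
| 5% | 6 | 0.033 | 0.046 | 0.061 | 0.114 |
| 5% | 30 | 0.446 | 0.545 | 0.631 | 0.816 |

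At 1% to 2% severe-only, the shortfall per cohort is 0.01 to 0.04.

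**The case against.** The strongest reply is that the gap is mostly theoretical. The severity scale is ordered, and a committee that stops for two moderate events would hardly wave through two severe ones; the intent is very probably moderate or worse.

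Most of the severe grade also maps to an SAE criterion. For important medical events the protocol says "These events should usually be considered serious". On hospitalization it says "When in doubt as to whether hospitalization occurred or was necessary, the AE should be considered serious". Section 10.3.2 further presumes SAEs to be at least possibly related unless another explanation is obvious, and one related SAE stops escalation. What remains is mainly transient loss of self-care judged non-serious.

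That remainder still falls under the catch-all. The SRC must review at least 48 hours of safety data before each escalation (Sections 4.5 and 6.5), and an investigator reviews 24-hour sentinel data in each cohort (Section 4.1).

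The calculations also look at one bullet in isolation. The chance that escalation actually proceeds wrongly also requires that the other criteria are not met and that the SRC does not act, so it is smaller and cannot be computed from the documents. The n = 30 rows assume a constant event rate from 2.7 to 40 mg/kg, and a second event in the fifth cohort comes too late to stop any planned escalation.

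All of this stands as a limit on the practical effect. It does not supply the missing words. The disability criterion for seriousness sets aside relatively minor events such as uncomplicated headache, nausea or vomiting even when they interfere with everyday life, so a severe non-serious event is possible. The catch-all restores the judgment that the numeric rule was meant to remove. Probable intent is a reason to write the intent down.

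**Conclusion.** The rule is wrong as written. It mandates a stop for two moderate events but not when severe non-serious events take the place of one or both. That conclusion rests on the text alone and needs no assumed rate.

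The practical effect is probably modest. What is lost is the automatic stop for severe non-serious events, while SRC discretion, the SAE criterion and the sentinel review remain. The figures depend on assumed rates, independent participants and, for the unconditional figures, a constant rate across doses. They describe how often this one bullet fires, not the risk that escalation continues unsafely. The change is still worth making, because it corrects a decision threshold in a first-in-human safety rule.

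**What to change.** In the adverse-event bullet of Protocol Section 4.6.1, insert *or severe* after *moderate*. Make the same change in the SRC charter if it repeats the rule; the charter is not among the documents reviewed. Leave the bullet's relatedness wording as it is, since the Assessment of Causality text in Section 10.3.2 defines a reasonable possibility more narrowly.

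The cost is two words in an amendment. No data, participants, analyses or SAP text change.
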